
regulated[15,16]. The morphology of mitochondria is altered in disease: mitochondria can shape into elongated tubules during mild stress and starvation. In contrast, acute severe stress frequently causes a dramatic mitochondrial fragmentation and decreased oxidative phosphorylation[16].

Recent studies performed on animal models have shown that some of the proteins responsible for the processes of fusion and fission are crucial for the proper muscle growth and function of mitochondria in muscle cells[15]. Therefore, alterations in mitochondrial dynamics often play a crucial role in skeletal muscle dysfunction and have been recently extensively studied in several myopathies[17]. Although it has been established that skeletal muscle regeneration parallels altered mitochondrial dynamics and biogenesis, the cells that mediate the remodelling of mitochondrial networks have not been yet thoroughly investigated[18]. Moreover, there is still lack of clear information about mitochondrial dysfunction in skeletal muscle weakness after critical illness.

Our group already adopted a method of satellite cell isolation and culture from human vastus lateralis biopsies and tested nutritional influences[19]. We have found in a pilot experiment that bioenergetic profiles of myotubes from patients with protracted ICU stay differ from healthy control, mostly by mitochondrial mass deficiency and reliance of remaining mitochondria on lipid-derived substrates[20]. In addition, we found out that 4 days of propofol exposure induces respiratory chain alterations (mostly fatty acid oxidation defect)[21], which we later managed to further characterize [22]. Long term significance of these findings to satellite cell ability to repair damaged muscle remains unknown.

STUDY HYPOTHESES AND AIMS

Hypothesis:

Critical illness induces damage to satellite cells in skeletal muscle that later impairs skeletal muscle structural and functional recovery and contributes to persistent weakness and failed functional outcome.

Aims of the project:

1. We will compare structural and functional (incl. bioenergetic) characteristics of satellite cells in acute, protracted and post-ICU phase in critically ill patients vs. control subjects.
2. We will test the hypothesis that structural and/or functional alteration of satellite cells correlate with gross muscle mass and power in survivors of critical illness.

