3. We will elucidate factors that influence bioenergetics and mitochondrial morphology of satellite cells (such as extracellular inflammatory milieu, drugs common in ICU as well as nutritional and anabolic factors).

METHODS

General methodological approaches

1. Clinical outcomes will be assessed by objective validated tests such as SF-36 questionnaire for the quality of life assessment, Medical Research Council Score of muscle power and 6 minutes walking test to measure aerobic performance.
2. Metabolic characteristics will be assessed at whole body level by hyperinsulinaemic euglycaemic clamps and at tissue level by vastus lateralis biopsies.
3. We will assess global mitochondrial indices of satellite cells by oxygen consumption measurement (production of ATP, uncoupling of inner mitochondrial membrane, maximal respiratory capacity of respiratory chain, glycolytic capacity and fatty acid oxidation). Simultaneously, we will measure production of reactive oxygen species and mitochondrial membrane potential. The changes will be assessed in various time intervals in the acute, protracted and post-ICU phase of critical illness.
4. We will analyze mitochondrial density, structure and organization of mitochondrial network in satellite cells, length of mitochondrial branches and connections in the acute, protracted and post-ICU phase of critical illness.

Design

Investigator initiated, prospective, controlled, cohort study with physiological end-points

Study subjects

Inclusion Criteria: All of the following must be present:

- Critically ill patients receiving mechanical ventilation, to be enrolled within 72 hours of admission, who are likely to need 7 days or more of ICU stay
- Sudden onset of disease, which can be determined in time (such as trauma, stroke, sudden cardiac arrest etc.)
- Informed consent signed by patient or patient's representative

Exclusion criteria: None of these shall be present

- Unlikely to survive 6 months
- Premorbid downslope functional trajectory or poor performance status (ECOG Gr. 3 or worse) or baseline functional status unknown
- Bleeding disorder (INR \geq 1.5 or PLT $<$ that would preclude muscle biopsies)
- Known mitochondrial disease
- Endocrine crisis as a reason for admission
- Pregnant women

Control subjects: Elective hip surgery patients with very good to excellent performance status, only limited to joint pain (ECOG 0)

Informed consent procedure

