All patients with capacity will be asked to provide a prospective written informed consent (See Appendix 3). For patients without capacity, a deferred consent procedure will take a place. In this case, an independent clinician will review and sign that the patient is lacking capacity and he/she fulfils all criteria to be enrolled to the study. The patient's next of kin will be informed about the study as soon as practical with the aid of information leaflet (Appendix 3). The patient will be asked to provide and sign informed consent as soon as he/she regains the capacity to do so. In case of consent refusal, patient's data will not be used in per-protocol analysis.

Study procedures

Eligible patients will be assessed at baseline, after 7 days and 6 months by clinical tests, metabolic tests and muscle biopsies as shown in table 1.

Test	Baseline	Day 7 or ICU discharge	6 months follow up	Note: Control subjects
Enrolment criteria, informed consent	x			x
Insulin clamps		x	x	x
Muscle biopsy	x	x	x	X
Functional performance test			x	x
Muscle mass by ultrasound	x	x	x	x

Table 1: Study procedures

Biopsies. Experimental group (= critically ill): Skeletal muscle samples (70 – 100 mg of muscle tissue) will be obtained from vastus lateralis muscle by needle biopsy technique (Bergström needle). *Control group (= orthopaedic patients):* Biopsies (> 100 mg of muscle tissue) will be taken from vastus lateralis muscle by open technique during surgery in control (hip replacement surgery)patients.

Isolation and cultivation of cells. Skeletal muscle cells will be isolated and cultured as previously described [19] (see **Figure 1**).

[figure not shown]

Figure 1. Primary human skeletal muscle cells. Myoblasts (A) and differentiated myotubes (B) under binocular inverse microscope and appearance of myoblasts (C) and myotubes (D) stained for desmin (AB 907 rabbit anti-desmin polyclonal antibody [Millipore, Billerica, MA, USA]) under confocal laser scanning microscopy. Source: published data of main proponent [19].

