Mitochondrial structure and membrane potential measurement. In parallel with OCR and ECAR analysis, mitochondrial structure will be determined. These parameters will be visualized and quantified in living cells via fluorescent microscopic tools in high resolution using Confocal Laser Scanning Microscopy with a 63x oil immersion objective (Leica TCS SP5 system, Leica Microsystems). Measurement will be based on accumulation of fluorescent dye inside mitochondria (MitoTrackerTM Green staining) which enables to determine number and length of mitochondrial branches. Simultaneously, a positively charged dye tetramethylrhodamine ethyl ester will be used to image active mitochondria with excitation/emission maximum 549/575 nm[24]. Intensity of fluorescence will be normalized to levels measured after MitoTrackerTM Green staining (see **Figure 3**).

[figure not shown]

Figure 3. Satellite skeletal muscle cells after staining with MitoTrackerTM Green (MTG; left), tetramethylrhodamine ethyl ester (TMRE; in the middle) and after staining of both agents (right). Positively charged dye TMRE (mitochondrial membrane potential dependent) is accumulated only in active mitochondria due to its

relative negative charge. Determination of mitochondrial membrane potential is performed after normalization to MTG fluorescence (mitochondrial membrane potential independent), which covalently binds to mitochondrial proteins by reacting with cysteine residues.

Acquired data will be analyzed using ImageJ™ (MacBiophotonics).

Power analysis and statistical plan

There is no formal primary outcome and hence no formal power analysis can be performed. The so far largest trials in the field have both 11 subjects with complete follow up [5,27] and in our trial we will have at least twice this number. Comparison of morphological and functional indices between the elective hip surgery patients (control cohort) and critically ill patients upon ICU admission will be determined using a Welch's unpaired T-test. Changes of these parameters in time (ie. from ICU admission to 6 months following ICU discharge) will be determined using a linear mixed-effects model with random intercept.

Direct access to source data/documents

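### The only named patient–control analysis is an unadjusted Welch t-test, although the groups come from different populations, have different performance-status limits and are not said to be matched on age or sex

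*Protocol*

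**What the plan says.** All references are to the protocol.

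- **Design:** "Investigator initiated, prospective, controlled, cohort study with physiological end-points". Nothing is randomised.
- **Analysis ('Power analysis and statistical plan'):** Welch's unpaired t-test is assigned to the "Comparison of morphological and functional indices between the elective hip surgery patients (control cohort) and critically ill patients upon ICU admission". The only other method is a random-intercept linear mixed model for change over time from ICU admission. No covariate is named for either.
- **Controls ('Study subjects'):** "Elective hip surgery patients with very good to excellent performance status, only limited to joint pain (ECOG 0".
- **Patients ('Study subjects'):** inclusion requires "Sudden onset of disease, which can be determined in time (such as trauma, stroke, sudden cardiac arrest etc". One exclusion reads "Premorbid downslope functional trajectory or poor performance status (ECOG Gr. 3 or worse) or baseline functional status unknown", which leaves stable ECOG 0, 1 and 2 eligible.
- **Matching:** no age or sex matching, and no age range, is given for either group.
- **Purpose ('Study hypotheses and aims'):** the hypothesis is causal: "Critical illness induces damage to satellite cells in skeletal muscle that later impairs skeletal muscle structural and functional recovery". Aim 1 compares "characteristics of satellite cells in acute, protracted and post-ICU phase in critically ill patients vs. control subjects".
- **Sampling ('Study procedures'):** in patients, muscle "will be obtained from vastus lateralis muscle by needle biopsy technique". In controls it is taken by open technique during the operation.

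**The concern.** A two-sample test on a non-randomised contrast answers whether two cohorts differ, not why. Here the eligibility rules themselves build in one difference: ECOG 1–2 can occur among patients and cannot occur among controls. The source populations make differences in age and sex plausible as well. Welch's test protects against unequal variances. It does nothing about a shift in means that was present before the illness.

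Because the hypothesis says that critical illness causes the damage, readers are likely to take this contrast as evidence of that effect. Poorer premorbid function in patients would look like damage. Older controls would hide damage. The two could also cancel. The Welch result alone would not show which of these had happened.

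**Working it through.** **1. Is Welch the only patient–control analysis named?** Yes. The mixed model is described for change over time, and Table 1 gives controls a single column with no repeat visits. The within-patient model is therefore outside this point.

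**2. Which numbers does the protocol supply?** Only that at least twice 11 subjects, 2 × 11 = 22, will have complete follow-up. That is a floor for 6-month completers, not the sample at ICU admission. The number of controls, the ages, the sex and ECOG mix, the SDs and the significance level are not stated. There is no figure to reproduce, and everything below is illustration.

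**3. Expected shift in the Welch contrast with no illness effect** (patients minus controls, in residual SD units, lower index = worse):

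shift = (age gap × slope per year) − (share of patients at ECOG 1–2 × their deficit)

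- Controls 15 y older, 0.02 SD/y, no ECOG difference: 15 × 0.02 = +0.30.
- No age gap, 50% of patients 0.6 SD lower: −0.5 × 0.6 = −0.30.
- Both of these: 0.30 − 0.30 = 0.
- 15 y gap with 30% of patients 0.3 SD lower: 0.30 − 0.09 = +0.21.

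**4. Simulated bias and rejection rate.** Assumptions: 22 v 22, no illness effect, two-sided 5%, residual SD 1, age SD 12 y, 70% v 50% male. Rows 1–4 use 6,000 runs each and row 5 uses 4,000. Regression is on group, age and sex with HC3 standard errors.

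| Assumed imbalance | Welch | Regression, all patients | Regression, ECOG 0 patients only |
|---|---|---|---|
| Age only (15 y, 0.02/y) | +0.30, 15.7% | 0.00, 4.4% | 0.00, 4.4% |
| ECOG only (50% at 0.6) | −0.30, 15.4% | −0.30, 12.8% | 0.00, 4.1% |
| Both (15 y; 50% at 0.6) | −0.01, 5.4% | −0.31, 11.6% | −0.01, 4.3% |
| Both (15 y; 30% at 0.3) | +0.21, 9.8% | −0.08, 5.0% | +0.01, 4.3% |
| ECOG (50% at 0.6) and controls 0.3 SD lower from joint limitation, no age gap | +0.01, 5.2% | +0.01, 4.4% | +0.32, 10.6% |

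Welch can be shifted either way, or look clean because two shifts cancel. Age and sex adjustment removes the age part but leaves the performance-status part. Restriction to ECOG 0 removes that part, but fails if controls' joint limitation affects the index. No single analysis is safe in every row, so the comparison is more informative when several are shown together.

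**5. Precision cost.** SE relative to an unadjusted 22 v 22 comparison is √[(1/n + 1/22)/(2/22)] × √[1/(1 − R²)], where R² = p(1−p)D²/[p(1−p)D² + 144], p = n/(n+22), n is the number of patients analysed and D is the age gap in years.

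- All patients, n = 22, p(1−p) = 0.25. D = 10: R² = 25/169, ratio 1.08. D = 15: R² = 56.25/200.25, ratio 1.18. D = 20: R² = 100/244, ratio 1.30.
- ECOG 0 only, n = 15 (30% dropped): 1.20, 1.30, 1.43.
- ECOG 0 only, n = 11 (50% dropped): 1.32, 1.42, 1.56.

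**The case against.** **Covariates and sensitivity sets usually belong in the SAP, which is not shown, and naming Welch does not bar an adjusted analysis.** This is true, and the mere absence of a covariate list would not be a finding. But the protocol itself names the test, and following it as written gives a confounded contrast. A later SAP also cannot use an ECOG grade that was never captured. Baseline function must be known and eligibility documented, but nothing requires the grade 0, 1 or 2 to be recorded.

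**The stakes are modest.** This stands. The protocol designates no primary outcome. The hypothesis concerns later recovery, and change over time is analysed within patients. The closing paragraph under 'Publication Policy' speaks of generating hypotheses, although it also expects the results to enable treatment strategies.

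**A reader might infer that the contrast is biased towards finding damage, or that its false-positive rate is the 15% or so in the illustration.** The protocol supports neither. It gives no distribution from which a direction or size follows, and 22 is not the admission sample.

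**A reader might also infer that the effect of critical illness should be judged from a regression restricted to ECOG 0 patients, since that column looks cleanest in the first four rows.** That goes too far. Those rows contain only confounders which that model handles. Controls are ECOG 0 apart from joint pain, so the shared label need not mean equal status, and the fifth row shows the restricted analysis then being the biased one. It is also costly. For an assumed true effect of −0.8 SD and a 15-year gap, its power is 43% v 45% for Welch (30% at 0.3 SD), or 36% v 69% (50% at 0.6 SD). It applies to ECOG 0 patients only. It belongs as a sensitivity analysis.

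**Needle v open biopsy** coincides exactly with group. No analysis of these data can adjust for it. It is a limitation to state, not a fault of Welch's test.

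**Conclusion.** The point holds as a cheap improvement. The protocol fixes an unadjusted test as its only named patient–control analysis, in a non-randomised cohort whose entry rules differ by group on performance status and state no age or sex matching. Differences in age, sex and premorbid function enter the contrast, and Welch's test cannot separate them from critical illness.

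Neither size nor direction can be derived from the document. Under the assumed inputs above, the shift in the Welch contrast ranges from −0.30 to +0.30 SD, including near zero through cancellation. These figures rest on 22 v 22 and on assumed slopes, shares and deficits, and they show only what is possible. The within-patient mixed model is not affected. Even with adjustment, the contrast remains a difference between cohorts.

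**What to change.** Keep Welch's test as the descriptive comparison and add to 'Power analysis and statistical plan':

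> Each index will also be compared by linear regression on group, age and sex with heteroscedasticity-robust (HC3) standard errors in all patients and controls. A sensitivity analysis will repeat this in patients with premorbid ECOG 0. Age, sex and premorbid ECOG grade (0, 1 or 2) will be recorded at enrolment and tabulated by group. Because biopsy technique (needle v open) and joint limitation in controls also differ by group and cannot be adjusted for, results will be reported as differences between cohorts, not as effects of critical illness alone.

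The cost is one paragraph and three recorded items. Recruitment and procedures do not change. The adjusted estimate is less precise: on the illustrative 22 v 22, the SE is about 8% to 30% larger for age gaps of 10 to 20 years. In the ECOG 0 analysis it is 20% to 43% larger with 15 patients, or 32% to 56% with 11. A larger admission sample would ease this but would not reduce bias. Two limits remain: age and sex adjustment does not remove differences in performance status, and the ECOG 0 restriction does not equalise joint limitation.
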